**Adverse Events**

- Otitis externa
  
- Cerumen impaction or ear foreign body requiring removal by a physician

**Serious Adverse Events**

- Death from any cause

An adverse event of otitis externa is defined as inflammation or infection of the ear canal resulting in pain, swelling, irritation, itching, or other related symptoms as diagnosed by the study audiologist or a physician. Adverse event severity is defined as:

- **Mild** if the symptoms are self-limited and resolve with interventions such as transiently limiting hearing aid use and/or the use of over-the-counter pharmacological therapies such as hydrocortisone cream or swimmer’s ear drops.
- **Moderate** if the symptoms require evaluation and management by a physician *and* the use of topical prescription pharmacological therapies such as antibiotic ear drops.
- **Severe** if the symptoms require evaluation and management by a physician and the use of oral or parenteral antibiotics.

An adverse event of a cerumen impaction or ear foreign body requiring removal by a physician is defined as a cerumen impaction and/or ear foreign body that cannot be routinely managed by the study audiologist and requires evaluation and management by a physician (typically an otolaryngologist). Adverse event severity is defined as:

- **Mild** if the cerumen impaction or foreign body is resolved without further need for therapy besides over-the-counter pharmacological therapies such as cerumenolytic drops.
- **Moderate** if there is an associated otitis externa requiring the use of topical prescription pharmacological therapies such as antibiotic ear drops.
- **Severe** if the cerumen impaction or ear foreign body results in a perforation of the tympanic membrane or an associated otitis externa requiring the use of oral or parenteral antibiotics.

AEs or SAEs will be defined as **unexpected** or **expected** based on the judgement of the field site PI in consultation with the study audiologist and/or study PI [name] (who is a board-certified otolaryngologist) based on the following definitions:

- **Unexpected** – nature, severity, or frequency of the event is not consistent with information about the condition under study or intervention in the protocol and consent form

- **Expected** – event is known to be associated with the intervention or condition under study.

Study-relatedness of AEs or SAEs will be based on the judgement of the field site PI in consultation with the study audiologist and/or study PI [name] based on the following guidelines:

- **Definitely Related:** The adverse event is clearly related to the investigational intervention – i.e., an event that follows a reasonable temporal sequence from administration of the study intervention, follows a known or expected response pattern to the suspected intervention, that is confirmed by improvement on stopping and reappearance of the event on repeated exposure and that could not be reasonably explained by the known characteristics of the subject's clinical state.
- **Possibly Related:** An adverse event that follows a reasonable temporal sequence from administration of the study intervention, that follows a known or expected response pattern to the suspected intervention, but that could readily have been produced by a number of other factors.
- **Not Related:** The adverse event is clearly not related to the investigational agent/procedure - i.e., another cause of the event is most plausible; and/or a clinically plausible temporal sequence is inconsistent with the onset of the event and the study intervention and/or a causal relationship is considered biologically implausible.

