## 7 Data collection and measurements

### 7.1 Audiometric assessment

The audiometric diagnostic battery will be conducted by a trained audiologist for all participants, regardless of treatment assignment. The diagnostic battery is based on current American Academy of Audiology guidelines. Cerumen management by the study audiologist will be performed as needed. Participants with more severe cerumen impactions that cannot be easily cleared by the study audiologist will be provided with over-the-counter cerumenolytic ear drops (e.g., Debrox, Murine) and advised to follow-up with their primary care provider or an otolaryngologist.

All audiometric testing will occur in a sound-attenuated booth. The WhisperRoom ([www.whisperroom.com/](http://www.whisperroom.com/)) was chosen due to its small footprint and lower weight compared to traditional metal sound booths.

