**Session B** occurs approximately 1-3 weeks after hearing aid fitting in order to allow for acclimatization to occur. If modifications are needed to the hearing aid fitting, they can occur and be documented in this or any subsequent sessions. During Session B, informal assessment of progress toward goals will be determined and needs for various hearing assistive technologies (HATs) will be assessed. HATs provide a more direct coupling of the sound source to the hearing aid, minimizing the negative effects of distance and background noise. Additional materials to support self-management are provided.

**Session C** occurs approximately 1-3 weeks after Session B. Short-term hearing aid outcomes are assessed and individually selected HATs are dispensed. Each participant will receive at least one HAT, depending on his or her specific goals, and outcomes of hearing aid use. These HATs may include the following or generally equivalent devices: Phonak ComPilot II (streaming device); Phonak ComPilot Air II (streaming device); Phonak TVLink II; Phonak clip-on mic; and/or the Phonak Roger System. Systematic orientation to HAT use is provided and additional self-management tools are dispensed.

**Session D** occurs approximately 1-3 weeks after Session C. Short-term outcomes of the comprehensive intervention approach, including use of hearing aids, HATs, and development of self-management skills, are assessed. Additional materials as needed to support self-management are provided as well as a supply of batteries.

**Booster Intervention/Interim Visits:** Scheduled semi-annual visits will capture audiologic outcomes and verify that hearing aids and HATs are functioning properly. Re-instruction in use of devices and hearing rehabilitative strategies will be provided during these visits. Booster sessions may be offered in a group format to allow for group rehabilitation for participants who are interested. We anticipate that unscheduled interim visits may also be required periodically (e.g., hearing aid malfunction), and these visits to trouble-shoot and/or repair malfunctioning hearing aids and/or HATs will be scheduled as needed if the issue cannot be resolved through a telephone conversation.

Full details of the hearing intervention can be found in the MOP.

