### 11.2 Adverse events

Study participation and exposure to the hearing aid intervention is expected to have a low risk of adverse events for the participant. At the same time, the age of the participants may naturally lead to numerous deleterious health outcomes. In order to efficiently collect safety information that is relevant to study participation, interventions, and procedures, detailed information concerning a **pre-specified set** of adverse events and serious adverse events will be collected and evaluated throughout the conduct of the trial.

An **adverse event (AE)** is an untoward medical occurrence, whether or not considered study-related, which occurs during the conduct of a clinical trial

A **serious AE (SAE)** is any AE that results in any of the following outcomes:

- Death
- Life-threatening
- Inpatient hospitalization or prolongation of existing hospitalization
- Results in persistent or significant disability or incapacity
- A *major* congenital anomaly or birth defect
- Important medical event that may not result in one of the above outcomes, but may jeopardize the health of the study participant or require medical or surgical intervention to prevent one of the outcomes listed above.

For this study, ***only the following adverse events and serious adverse events will be recorded and reported:***

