5.	.1	Preliminary Analysis	9
5.	.2	Evaluation of Assumptions 1	0
6.	An	alysis Populations1	0
6.	.1	Intent-to-Treat Population	0
6.	.2	Per Protocol and Complier Population	1
7.	Sta	tistical Analysis1	1
7.	.1	General Considerations	1
7.	.2	Primary Outcome 1	2
7.	.3	Primary Analysis 1	3
7.	.4	Sensitivity Analyses of the Primary Outcome	3
7.	.5	Secondary Outcomes	4
7.	.6	Exploratory Analyses of the Primary Outcome 1	4
7.	.7	Adjustment for Multiple Comparisons1	5
7.	.8	Additional Outcomes1	5
8.	Glo	obal cognitive function factor score1	5
9.	CC	VID-19 Considerations	6
10.	Sot	ftware and Statistical Programming1	6
11.	Re	ferences 1	6

LIST OF ABBREVIATIONS

ACTIVE	Advanced Cognitive Training for Independent and Vital Elderly study
AD	Alzheimer's Disease
APOE	Apolipoprotein E
ARIC	Atherosclerosis Risk in Communities
CDR	Clinical Dementia Rating
dB	decibels
DSMB	Data and Safety Monitoring Board
HealthABC	The Health, Aging, and Body Composition Study
HRQL	Health-Related Quality of Life
ITT	Intention-to-treat
MCI	Mild Cognitive Impairment
MMSE	Mini-Mental State Exam
SD	Standard deviation

1. Introduction

ACHIEVE is a randomized controlled trial. Approximately 850 participants will be randomly assigned to one of two conditions and followed for three years: hearing intervention with hearing aids or successful aging intervention. Participants will be community-dwelling adults aged 70-84 years with audiometric hearing impairment defined as a four-frequency (0.5, 1, 2, 4 kHz) pure-tone average threshold in the better-hearing ear of \geq 30 decibels (dB) and <70dB. This document gives details of the planned statistical analyses.

2. Background

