7.8 Additional Outcomes

Additional outcomes that will be examined include measures of social and physical function, physical activity, and HRQL. Analyses of these outcomes are considered exploratory in nature and will not be viewed as providing confirmatory tests of hypotheses. There will be no adjustment for multiple comparisons and p-values will be provided for descriptive purposes only.

Outcomes will be modeled continuously (outcomes transformed to account for non-normality if necessary) or categorized according to clinically-relevant cut-points²⁹. Intervention conditions will be compared using the same approach adopted for the primary analysis.

8. Global cognitive function factor score

The global cognitive function factor score uses all available cognitive test data, has interval-level properties³⁰, is internally consistent using ARIC data (Cronbach's alpha=0.87), has minimal floor or ceiling effects³¹, and demonstrates reliable measurement precision over a broad range of cognitive ability. We have previously demonstrated criterion validity and established cut-points for clinically relevant impairment of the general cognitive performance factor score³¹. We have since extended the harmonization to 26 studies with over 60,000 people, most of which have longitudinal data. Using simulation, we verified the cognitive metric is the same across datasets³¹. We compared precision of our approach with other approaches to combining data using external data: underscoring enhanced precision in a sample of 10,875 persons in 9 datasets, our approach required the smallest sample size to detect cognitive decline with 80% power (N=232) compared to using only the MMSE (N=277) or summarizing available tests into a z-score (N=291)^{27, 32}. We further validated the approach against change in hippocampal volume and overall cortical thickness²⁷. The approach is consistent with other harmonization techniques and has been used in several other published studies ^{25, 31-36} including demonstrations that the factors have the same meaning across datasets with different cognitive tests ^{15, 25, 31-35, 37-40}.

9. COVID-19 Considerations

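### No by-arm analysis of the recorded harms is planned, and a crude count of otitis externa could mislead because the hearing arm has more scheduled contact with the audiology service

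*Protocol*

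**What the plan says.** **What is recorded.** Protocol 11.2 states that "only the following adverse events and serious adverse events will be recorded and reported". Its list has two ear events and one serious event, death from any cause.

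**Who determines the ear events.** Otitis externa is inflammation or infection of the ear canal with pain, swelling "or other related symptoms as diagnosed by the study audiologist or a physician". Mild cases settle by themselves or with over-the-counter care; moderate and severe cases require a physician. The other ear event is a cerumen impaction and/or "ear foreign body that cannot be routinely managed by the study audiologist and requires evaluation and management by a physician". Protocol 7.1, which covers audiometry in both arms, adds: "Cerumen management by the study audiologist will be performed as needed". The same paragraph says that impactions the audiologist cannot easily clear are given drops and directed to primary care or an otolaryngologist.

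**Contacts.** Protocol 9.1 gives the hearing arm Sessions A to D, and then: "Scheduled semi-annual visits will capture audiologic outcomes and verify that hearing aids and HATs are functioning properly". Unscheduled repair visits may be added. Controls see a health educator (Protocol 9.2) and have audiometry at months 12, 24 and 36 (Table 3).

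**Analysis.** The SAP introduction says: "This document gives details of the planned statistical analyses". It has no safety section. SAP 7.8 reads: "Additional outcomes that will be examined include measures of social and physical function, physical activity, and HRQL". Death enters only through the attrition assumption (5.1) and the handling of imputed scores (7.3). Protocol 12.2 has no harm analysis either. Protocol 11.2 provides for DSMB review and for reporting to the IRBs and the NIA.

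**The concern.** The trial tests a device against an attention control, and the two ear events are its only device-related harm data. With no planned comparison, what is reported, and how, is left to choices made after the data are seen.

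The obvious default is a count of recorded events by arm. For otitis externa that count depends partly on how often a participant meets the person whose diagnosis makes an event. Mild cases are the ones most exposed, since they need no physician. If the hearing arm meets the audiologist more often, it can show more otitis externa with no difference in true incidence, and the excess could be read as an effect of hearing aids. DSMB review is oversight during the trial and does not supply a pre-specified estimate by arm.

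**Working it through.** The documents give no event rate, power or sample-size figure for harms, so there is nothing to reproduce. The contact counts come from Table 3. The rest is illustration on stated assumptions.

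**Step 1. Scheduled post-randomisation contacts.**
- Hearing arm: Sessions A to D (Visits 2 to 5) plus six semi-annual visits (Visits 6 to 11), 4 + 6 = 10. As a cross-check, the hearing aid data log is marked at Visits 3 to 11 (9), and Session A adds one.
- Controls: audiometry at Visits 7, 9 and 11, so 3.
- Ratio: 10/3 = 3.3.
- Adverse-event assessment: Visits 2 to 11 in both arms, so 10 each. At 10 − 3 = 7 of the controls' visits no audiologist is scheduled.

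**Step 2. Pandemic.** In-person visits stopped in mid-March 2020 (Protocol 19.1) and in-person testing resumed in June 2021 (SAP 7.1). Removing visits that fall in that window, for randomisation from November 2017 to October 2019, and keeping the delayed in-person Year 3 visit, leaves 7 to 9 contacts against 1 to 3. The ratio is 3.0 to 7.0, depending on the month of randomisation.

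**Step 3. Effect on recorded otitis externa when true rates are equal.** Assumptions, none from the documents: 5 episodes per 100 person-years in both arms; each visible for *w* = 2 or 4 weeks; the audiologist finds any episode visible at a contact; a fraction *p* is recorded through a physician, equally in both arms. From the documents: 977/2, about 488 per arm, and 3 years (156 weeks).

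- True episodes per arm: 488 × 3 × 0.05 = 73.2.
- Chance of audiologist detection: *f* = contacts × *w*/156. At 2 weeks, 20/156 = 0.128 against 6/156 = 0.038. At 4 weeks, 0.256 against 0.077.
- Expected recorded events: 73.2 × [*p* + (1 − *p*)*f*].
- False rejection: probability that an exact conditional binomial test of equal rates gives p < 0.05, with Poisson counts.

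| *p* | *w* (weeks) | Hearing v control | Ratio | False rejection |
|---|---|---|---|---|
| 0 | 2 | 9.4 v 2.8 | 3.3 | 37% |
| 0 | 4 | 18.8 v 5.6 | 3.3 | 72% |
| 0.25 | 2 | 25.3 v 20.4 | 1.24 | 9% |
| 0.25 | 4 | 32.4 v 22.5 | 1.44 | 22% |
| 0.50 | 2 | 41.3 v 38.0 | 1.09 | 5% |
| 0.50 | 4 | 46.0 v 39.4 | 1.17 | 9% |
| 0.75 | 2 | 57.2 v 55.6 | 1.03 | 4% |
| 0.75 | 4 | 59.6 v 56.3 | 1.06 | 5% |

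The formula treats contacts as separate chances. Sessions A to D are close together, so a 4-week episode can span two of them. With the sessions placed at weeks 2, 4, 7 and 9 the 4-week ratios fall to 2.75 (*p* = 0) and 1.33 (*p* = 0.25). False rejection also depends on the assumed rate: with *p* = 0 it runs from about 7% (2 per 100 person-years, 2 weeks) to 97% (10 per 100, 4 weeks).

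**Step 4. Cerumen.** Two provisions pull in opposite directions. Clearance by the audiologist keeps an impaction out of the count, because the event must be one that "cannot be routinely managed by the study audiologist and requires evaluation and management by a physician". Yet the audiologist also directs difficult impactions to a physician, which creates the event. The documents do not show which effect is larger.

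**The case against.** The strongest reply is that controls are not under-observed. Adverse events are asked about at every visit in both arms, and a physician's diagnosis counts as fully as the audiologist's. That stands, and it rules out the reading that controls are assessed 3 times against 10. It also makes the 3.3-fold ratio the extreme case: the table shows the bias shrinking quickly once physicians record a quarter or more of episodes.

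Nor is a contact the same as an ear examination. At months 6, 18 and 30 Table 3 lists a data log and an outcome questionnaire, with real-ear measures only if reprogramming is needed. Boosters may be run in groups (Protocol 9.1), delegated staff may take part (Protocol 15.1), and pandemic visits were remote. Ten is therefore a planned maximum of scheduled contacts, although unscheduled repair visits can add to it.

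A reader might infer that cerumen impaction is understated in the hearing arm, giving opposite biases for the two ear events. The documents do not support that: the clearance sentence sits in the audiometry section that applies to both arms, Section 9.1 does not mention wax clearance, and onward referral works the other way. A reader might also take moderate and severe otitis externa as free of the problem, but an audiologist who sees an inflamed canal can send the participant to a physician.

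Finally, the DSMB charter and manual of procedures were not available and may say more about safety monitoring. They may supplement the SAP, but they do not put a by-arm analysis in it. None of these replies fills that gap.

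**Conclusion.** The concern holds in a limited form. That no by-arm analysis of the three listed events is specified follows from the SAP and Protocol 12.2 without any assumption. So does the difference in scheduled contact, up to 10 against 3, as a planned figure.

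That a crude otitis externa count could mislead follows from the event definition combined with that difference. That it would mislead does not follow. Under equal true rates the illustrative ratio runs from about 1.03 to 3.3, governed by the share of episodes reaching a physician, which the documents do not give. For cerumen no direction can be claimed. Recording of death does not depend on audiologist contact, so for that event only the missing analysis matters.

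This is a gap in planned harm reporting that should be closed. It does not affect the primary analysis.

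**What to change.** Add a short safety section to the SAP, with a matching sentence in Protocol 12.2:

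1. By randomised arm, report participants with an event and events per person-year for otitis externa, for cerumen impaction or foreign body, and for death, with rate ratios and 95% confidence intervals.
2. For otitis externa, add a comparison limited to events found at the month 12, 24 and 36 audiometry visits that both arms have. List events found at hearing-arm-only contacts separately. Show moderate and severe events as less dependent on audiologist contact, but not independent of it.
3. State that audiologist contact was unequal by design and that crude ratios for both ear events carry that caveat. Do not describe the cerumen ratio as a lower bound.

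The cost is one SAP section and a few tables, with no new visits. The restricted comparison will have fewer events and wider intervals. It also relies on the Adverse Events Form holding the date or visit of detection, which should be confirmed because the documents do not list the form's fields. No change to event definitions or clinical management is proposed.

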### **Unanticipated Problems**

An unanticipated problem is defined as an incident, experience, or outcome that meets all of the following criteria:

- Unexpected – in terms of nature, severity, or frequency given the procedures and interventions used in the ACHIEVE study as described in the protocol and informed consent given the characteristics of the study population
- Possibly or definitely related to the participation in the ACHIEVE study
- Suggests that the research placed the participant or others at a greater risk of harm (including physical, psychological, economic, or social harm) than was previously known or recognized

Some but not all adverse events may qualify as unanticipated problems.

The DSMB will review all recorded treatment-emergent adverse events and all serious adverse events (SAEs) from this pre-specified list and will provide a report to the Steering Committee and to the local IRBs. An SAE that is ***unexpected and possibly or definitely related to study participation or study intervention*** will be reported within 48 hours by the sites to the local IRB and the PI to the NIA and DSMB.

Adverse events and serious adverse events will be recorded on the electronic Adverse Events Form per study instructions. Additionally, for ***unexpected and possibly or definitely related***

**serious adverse events only**, sites will record a narrative description of the serious adverse event, including any relevant lab test results and dates.

All completed AE forms will be forwarded promptly to the Coordinating Center where they will be reviewed for completeness by the Coordinating Center staff and the ACHIEVE Principal Investigator ([name]). In particular, the Principal Investigator will assure that documentation of each event is adequate to permit accurate inferences regarding causation (e.g., temporal associations, onset, course, response to patient or physician intervention, alternative etiologies) and severity.

Full details of procedures for reporting adverse events can be found in the MOP.

## 12 Statistical considerations

### 12.1 Sample size

**Aim 1:** Comparison of hearing rehabilitative intervention versus successful aging control intervention for 3-year cognitive decline

Our sample size calculation is based on the primary outcome, the change in the Global Cognitive Function Factor Score from baseline to year 3. Estimates are based on the rate of change in the global cognitive function factor score from the first third of participants in the ongoing ARIC Visit 6 study (2016 to 2017) in addition to data from other representative studies with similar cohort characteristics as ARIC/ACHIEVE (i.e., ACTIVE and HealthABC). We also take into account assumptions regarding the rate of loss to follow-up as well as the rate of cross-over, where participants in the successful aging control group begin to wear hearing aids and participants in the hearing intervention group stop wearing the devices.

We based these calculations on a t-test comparing groups on change from baseline at 3 years to align with the primary analysis (a mixed effects model treating time as categorical) and aimed to achieve 90% power using a 2-sided test with a  $p=0.05$  significance level. We conservatively chose parameter estimates that fell within the mid-range of observed values from these studies.

Parameter assumptions include:

- Change in global cognitive function factor score in the control group per year:  
Estimated at -0.08 standard deviations (SD)/year (corresponding to -0.24 SD in 3 years)
- Standard deviation of change in global cognitive function factor score per year:  
Estimated at 0.09 (corresponding to 0.27 at 3 years)
- Drop-in/Drop-out: Estimated as a net total of 15% (drop-in + drop-out) for the 3-year study. This value is conservative. We assumed immediate drop-in/drop-out rather than later drop-in/drop-out (i.e., 1-2 years into the study) which would have less impact on reducing the observed effect size. We will continue to optimize the design to keep both

drop-in and drop-out rates low (e.g., rigorous training for active group vs. energized successful aging group promised free hearing aids at trial completion). Among 13 participants in the ACHIEVE-Pilot study who were randomized to the hearing intervention and have since been followed to 1 year, we did not observe any drop-out (discontinuation of hearing aid use) at 1 year (12 participants reported > 8 hours of hearing aid use/day and 1 participant reported 4-8 hours use/day). Similarly, drop-in rates will likely be minimized because all participants in the successful aging group are informed that they will receive free hearing intervention after 3 years of follow-up (out-of-pocket costs for hearing aids are otherwise currently ~\$4700 and are rarely covered by insurance). Rates of uptake of hearing aid use remain low in the community. In the HealthABC study among individuals with hearing loss in the inclusion range for the ACHIEVE study, rates of hearing aid uptake were ~3-4% per year.

- Missing data/withdrawal from competing events (e.g., mortality not associated with dementia): Estimated at 10%/year (corresponding to 27% in 3 years)

Based on these parameters and with 850 total individuals randomized, we will have 90% power to detect a 35% difference in annual cognitive decline between the hearing intervention vs successful aging intervention at 3 years follow-up.

**Aim 2:** For the secondary outcome of incident cognitive impairment, a dataset was constructed of participants in the ARIC cohort who had comparable characteristics to the individuals enrolled in ACHIEVE, did not exhibit signs of cognitive impairment at the baseline, and who were monitored over a period of 5 to 8 years. The observed rate was 50 cases of incident cognitive impairment per 1000 person-years. Assuming a 30% reduction in the hearing intervention condition and a 25% loss of person-time due to attrition, the planned analysis would have 80% power to detect a hazard ratio of 0.54 when using a 2-sided test and  $p < 0.05$ .

